11.4. TESTING/VALIDATION PLAN

Data will be periodically reviewed by the cross functional team and issues will be addressed by Clinical Data Management.

11.5. SOFTWARE

SAS® software version 9.4 or higher will be used to perform statistical analyses unless otherwise specified.

12. STATISTICAL METHODS OF ANALYSES

12.1. GENERAL PRINCIPLES

In general, summaries will be performed descriptively by treatment group. Continuous, quantitative (absolute values at each timepoint and change from baseline if applicable) variable summaries will include the number of subjects (N) with non-missing values, mean, standard deviation (SD), standard error (SE) of the mean, median, minimum, and maximum values.

Categorical, qualitative variable summaries will include the frequency and percentage of subjects in the particular category. In general, the denominator for the percentage calculation will be based upon the total number of subjects in the trial population for the cohorts.

All statistical tests will be two-sided and tested at statistical significant level of 0.05. P-values will be rounded and displayed in three decimals. If a p-value is less than 0.0001, it will be shown in tables as <0.0001. Confidence intervals will be 2-sided 95% confidence intervals, unless stated otherwise.

Unless otherwise specified, all summaries including by-visit summaries will be analyzed for the treatment period (Week 1 to Week 38).

12.2. SCREEN FAILURE

Reasons for screen failure and number of screen failure subjects will be summarized.

12.3. DISPOSITION

The number and percentage of subjects for each of the following categories will be summarized by treatment group:

- Intent-To-Treat population
- Subjects included in the Safety population
- Subjects who completed the 38-week randomized treatment period
- Subjects who discontinued early from the 38-week randomized treatment period and reasons for discontinuation
- Subjects rolling into the open-label extension trial (TCH-306 EXT)
- Subjects who entered the post-treatment safety follow-up period and did not enroll in the open label extension trial

12.4. PROTOCOL DEVIATIONS

Protocol deviations will be categorized as major and minor per the protocol deviation plan (v 3.0 dated 07 November 2023).

Major protocol deviations will be summarized by deviation category for all subjects in the ITT population. A by-subject listing of all protocol deviations will be provided.

12.5. INVESTIGATIONAL PRODUCT ADMINISTRATION

12.5.1. Extent of Exposure

The following parameters of the trial drug will be summarized and listed:

- Total duration of treatment (weeks)
- Total number of actual doses
- Actual total dosage (mg hGH)
- Actual average dosage received (mg/week)

Summary statistics per treatment group will be tabulated overall and by dosing group for the Safety Analysis Population.

12.5.2. Measurement of Treatment Compliance

Descriptive statistics for trial drug compliance will be presented by treatment group for the Safety Analysis Population.

The number of injections and cumulative dose per subject administered and duration of exposure by treatment group will be summarized. Treatment compliance will be calculated as total number of actual dose received divided by total number of planned dose expected over specified period will also be displayed.

12.5.3. Dose Adjustment

A descriptive summary including the frequency and percentages of subjects by each group will be presented for following dose adjustments categories for titration and maintenance period, separately:

- Planned Titration
- IGF-1
- Rechallenge
- AE
- Other

12.6. DEMOGRAPHIC AND BASELINE CHARACTERISTICS

Descriptive summaries will be provided for demographic and baseline characteristics on ITT and Per-protocol population, including but not limited to:

- Age (years)
- Age category (< 30, ≥ 30 - ≤ 60 and > 60 years)

- Sex (male, female)
 - Females (on oral estrogen, not on oral estrogen)
- Race
- Ethnicity
- Region
 - North America
 - Europe
 - Asia-Pacific
- Weight (kg)
- Body mass index (BMI) (kg/m²)
 - < 25 kg/m²
 - 25 ≤ - < 30 kg/m²
 - 30 ≤ - < 35 kg/m²
 - 35 ≤ - < 40 kg/m²
 - ≥ 40 kg/m²
- Body mass index (BMI) SDS
- IGF-1, IGF-1 SDS:
 - IGF-1 SDS < -2.0
 - IGF-1 SDS -2.0 ≤ - < -1.0
 - IGF-1 SDS -1.0 ≤ - < 2.0
 - IGF-1 SDS 2.0 ≤ - < 2.5
 - IGF-1 SDS 2.5 ≤ - < 3.0
 - IGF-1 SDS ≥ 3.0
- IGFBP-3, IGFBP-3 SDS
- Etiology of GHD:
 - Structural hypothalamic-pituitary defect
 - Pituitary tumor
 - Hypothalamic-pituitary surgery
 - Cranial irradiation
 - Traumatic brain injury
 - Genetic

- Other
- GHD Onset:
 - Childhood onset
 - Adulthood onset
- Pituitary Deficiencies:
 - GHD only
 - GHD and additional pituitary axis deficiencies
 - a. Adrenal Deficiency
 - b. Thyroid Deficiency
 - c. Gonadal Deficiency
 - d. Vasopressin Deficiency
- Time (yr) since diagnosis of GHD

12.7. MEDICAL HISTORY

Medical history will be coded using the Medical Dictionary for Regulatory Activities (MedDRA) and will be summarized by system organ class and preferred term. The most current March version of the dictionary will be used.

12.8. PRIOR AND CONCOMITANT MEDICATION

Prior medication is defined as any medication started before the date of the trial drug administration (medication start date prior to the first dose date).

Concomitant medication is defined as any medication taken during the treatment period defined as medication end date on or after the date of the trial drug administration or ongoing.

Both prior and concomitant medications will be coded to ATC level 4 (Chemical Subgroup) and ATC level 3 (pharmacologic class) based on route and indication using World Health Organization (WHO) Drug Dictionary. The most current March version of the dictionary will be used. If a subject took a specific medication multiple times or took multiple medications within a specific therapeutic class, that subject will be counted only once for the coded drug name or therapeutic class in summary tables. Prior and concomitant medications will be summarized overall and by treatment groups in tables for the Safety Analysis Population and will also be presented in a listing.

12.9. PRIOR AND CONCOMITANT PROCEDURES

Prior procedure is defined as any procedure started before the first date of the trial drug administration (procedure start date prior to the first dose date).

Concomitant procedure is defined as any procedures completed on or after the date of the trial drug administration (procedure end date on or after the dose date [or ongoing]).

Prior and concomitant procedures will be coded using the Medical Dictionary for Regulatory Activities (MedDRA) and will be summarized by overall and by treatment groups in tables for the Safety Analysis Population and will also be presented in a listing. The most current March version of the dictionary will be used.

12.10. EFFICACY ANALYSIS

Efficacy analyses will be conducted on the ITT population according to the randomized treatment assignment.

12.10.1. Analysis of Primary Efficacy Endpoint

Population: The target trial population comprises adult subjects with GHD and who meet the inclusion and exclusion criteria as specified in the Protocol. The analysis population is the Intent-To-Treat population as defined in Section 10.3 who have baseline trunk percent fat assessed by DXA.

Variable: The variable is the primary efficacy endpoint, change from baseline in trunk percent fat as assessed by DXA at Week 38 (Study day 240 to 295).

Handling of intercurrent events (ICEs) and missing data: Treatment policy will be used to handle ICEs where all subjects should be followed to collect the efficacy outcome regardless of intercurrent events, including treatment discontinuation or taking rescue or prohibited medications. Multiple imputation method will be used to impute the missing data if a subject is missing primary efficacy endpoint of change from baseline in trunk percent fat. See details in Section 11.2.6.

Population level summary: Treatment difference between lonapegsomatropin vs. Placebo in the change from baseline to Week 12 or Week 38.

Estimator: The difference in change from baseline at Week 38 in trunk percent fat will be estimated by the primary analysis of ANCOVA model adjusted for unequal variance, with multiple imputation for missing data as described in Section 11.2.6. The ANCOVA model will include treatment arm, region (North America, Europe, Asia-Pacific), baseline age group, gender, concomitant oral estrogen at screening in female subjects (yes vs. no), and AGHD onset (adult vs. childhood) and baseline trunk percent fat as a covariate.

For the primary efficacy analysis, a 2-sided 95% confidence interval will be calculated for the difference in least square means between the 2 treatment groups [lonapegsomatropin treatment minus placebo] at Week 38.

The absolute values and mean change from baseline of the primary endpoint variable by visit will be presented by treatment group with descriptive statistics.

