	
Categorical data will be presented using counts and percentages of subjects. Continuous variables will be presented using number of subjects, mean, standard deviation (SD), standard error (SE), median, minimum, and maximum.
 
The ANCOVA model will include treatment arm and dose group as factors, baseline trunk percent fat as a covariate and additional factors that may include region (Japan vs. all regions except Japan), baseline age group, sex, concomitant oral estrogen at screening (yes vs. no), diabetes mellitus (yes vs. no), and AGHD onset (adult vs. childhood). The daily somatropin product arm will be included in the ANCOVA model, but no formal statistical testing will be performed on this arm. The 95% confidence intervals will be calculated for the mean treatment differences between lonapegsomatropin vs. placebo and lonapegsomatropin vs. daily somatropin.
 
Similar ANCOVA models with multiple imputation will be applied to analyze secondary efficacy endpoints, with corresponding baseline value as a covariate.
 
To control familywise error rate at level of 0.05, the secondary endpoints will be adjusted by Hochberg procedure only if the test for the primary endpoint (lonapegsomatropin vs. placebo) is statistically significant.
 
Reporting of the safety data will be descriptive. The safety parameters include AEs, clinical laboratory, immunogenicity data, vital signs, ECG parameters, and other safety parameters.
 
Details of statistical methods will be provided in the Statistical Analysis Plan (SAP).

SAMPLE SIZE DETERMINATION	
This trial is powered for the efficacy comparison of lonapegsomatropin versus placebo. The daily somatropin product arm is included as a calibration arm and not powered for formal comparison.
 
Approximately 240 subjects will be randomized in a 1:1:1 ratio to once-weekly lonapegsomatropin, once-weekly placebo, or daily somatropin product.
 
A sample size of 80 subjects per arm in the lonapegsomatropin and placebo arms will provide 90% power to detect a treatment difference of 1.9% between once-weekly lonapegsomatropin and placebo for the primary endpoint of change from baseline in trunk percent fat at Week 38 at the 2 sided 5% significance level, with the assumption of a common SD of 3.7%.

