7.1.2. Measures Taken to Minimize Bias

Once all data and results determining the subject eligibility are available and reviewed by the Investigator and Medical Monitor, the subject will be centrally randomized to 1 of 3 treatment arms: either once-weekly lonapegsomatropin, (N = 80), once-weekly placebo (N = 80) or daily somatropin product (N = 80), in a 1:1:1 ratio. In all regions except Japan, the following stratifications will be applied:

1. Dosing group.
2. In the “ ≥ 30 to ≤ 60 years old (no oral estrogen)” dosing group, randomization will be further stratified by sex.
3. Diabetes mellitus status.

In Japan, randomization will be stratified by dosing group only.

All subjects' visits should be performed in the morning to ensure fasting status. Also, DXA assessments should be performed in a similar setting (time and hydration status) at each visit, using the same approved DXA machine throughout the trial.

Additionally, all efforts will be made to keep missing data to a minimum, including the following:

1. Investigators will be trained about the importance of subject retention.
2. Investigators will be instructed to encourage subjects to complete all trial visits, until they complete the trial.

3. Investigators will be trained to collect the reason for missing data when it does occur.
4. The Informed Consent Form (ICF) will include a statement educating subjects about the scientific importance of their data, even if they discontinue study drug.
5. Special efforts will be made to provide assistance to subjects who might discontinue due to travel or cost barriers, such as offers of transportation to the clinic.
6. Visit windows allow flexibility for clinic attendance (see Section [10.2.2.1](#) and Section [10.2.2.2](#)).
7. Every effort will be made to contact subjects/caregivers or other family members to maintain contact with the clinic.

Subjects will be identified by a Subject Number (allocated at screening) consisting of 5 digits to indicate the site and 3 digits specific for the subject.

For more details on risk-based monitoring, please refer to Section [15.5.1](#).

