14.4.1. Definition of the Estimand and Estimator for Primary Analysis

Population: the treatment effect is to be estimated for the Intent-To-Treat population of adult subjects with GHD as defined by the protocol inclusion/exclusion criteria.

Primary endpoint: efficacy is to be measured using the primary endpoint of change from baseline in trunk percent fat (as assessed by DXA) at Week 38.

Handling missing data/Intercurrent events (ICEs) missing reasons will be taken into considerations into multiple imputation. The Markov Chain Monte Carlo (MCMC) method will be used to impute the missing data, under the multivariate normality assumption to impute the missing data by treatment arm and dose group. Details will be provided in the SAP.

The difference in change from baseline at Week 38 in trunk percent fat will be estimated by the primary analysis of ANCOVA model, with multiple imputation for missing data. The ANCOVA model will include treatment arm, dose group, diabetes mellitus, and region (Japan vs. all regions except Japan) as factors, and baseline trunk percent fat as a covariate. Additional factors may include, baseline age group, sex, concomitant oral estrogen at screening (yes vs. no), and AGHD onset (adult vs. childhood). The daily somatropin product arm will be included in the ANCOVA model, but no formal statistical testing will be performed on this arm.

Subgroup analyses of the primary efficacy endpoint will be performed to determine whether treatment effects are consistent across clinically meaningful subgroups. The difference in change from baseline at Week 38 in trunk percent fat and their 95% confidence intervals will be displayed in a forest plot. Subgroups will include but not limited to the following: region, age group, gender and diabetes mellitus status.

Details on the analyses including derivation, handling of missing data, statistical method, sensitivity analyses including per-protocol analysis and subgroups will be provided in the SAP.

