2. TRIAL DESIGN

Trial TCH-306 (foresiGHt) is a multicenter, randomized, parallel-arm, placebo-controlled (double-blind) and active-controlled (open-label), Phase 3 trial to assess the efficacy and safety of lonapegsomatropin in adults with growth hormone deficiency. The length of this trial will be 38 weeks. Approximately 240 subjects meeting the eligibility criteria will be randomized in a 1:1:1 ratio to the following 3 treatment groups:

- Approximately 80 subjects to once-weekly lonapegsomatropin
- Approximately 80 subjects to once-weekly placebo
- Approximately 80 subjects to daily somatropin product

Randomization will be stratified as follows:

[figure not shown]
- Dosing group
 - Group 1: Oral estrogen intake (any age) or < 30 years old
 - Group 2: ≥ 30 to ≤ 60 years old; no oral estrogen intake
 - Group 3: > 60 years old; no oral estrogen intake
- In the Dose group 2 (≥ 30 to ≤ 60 years old; no oral estrogen), randomization will be further stratified by sex.
- Diabetes mellitus status

In Japan, randomization will be stratified by dosing group only.

After approximately 240 subjects have been enrolled under protocol amendment 2, enrollment in Asian countries will continue under amendment 4. To support applications across various countries, a total of approximately 282 subjects are expected to be enrolled in the trial.

This trial includes a screening period up to approximately 6 weeks, a treatment period of 38 weeks and a safety follow up period of 4 weeks.

A schematic of the trial is presented in [Figure 1](#) and a Schedule of Events in [Table 1](#).

Figure 1: TCH-306 Trial Design

W = Week; N = Number

Table 1: TCH-306 Schedule of Events

Visit	Screening (-6 to Week 1) ^a	Visit 1 (First Dose) (Week 1) ^a	Visit 2 (Titration) (Week 4)	Visit 3 (Titration) (Week 8) ^b	Visit 4 (Titration; Start of Maintenance Dose) (Week 12)	Visit 5 (Week 17)	Visit 6 (Week 28)	Visit 7 (Week 38 + 4 weeks) Early Term., EOT ^c
Weekly Visit Window	– 2 weeks	NA	-	-	-	+/- 1 week	+/- 1 week	+ 1 week
Once-weekly lonapegsomatropin or placebo visit days:	NA	Pre-dose	4-5 days post-dose (96 – 120 h post-dose +/- 3 h)	4-5 days post-dose (96 – 120 h post-dose +/- 3 h)	4-5 days post-dose (96 – 120 h post-dose +/- 3 h)	Pre-dose (144 – 168 h post-dose +/- 3 h)	1-3 days post-dose (24 – 72 h post-dose +/- 3 h)	4-5 days post-dose (96 – 120 h post-dose +/- 3 h)

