12.10.2. Analyses of Key Secondary Efficacy Endpoint(s)

Secondary efficacy variables include the following 2 key secondary endpoints with alpha-protection. The treatment effect of lonapegsomatropin compared with placebo will be tested for the alpha-protected secondary endpoint using a fixed sequence testing procedure described in Section 12.10.3.

- Change from baseline in total body lean mass at Week 38 (as assessed by DXA)
- Change from baseline in trunk fat mass at Week 38 (as assessed by DXA)

For the statistical method of analyzing the secondary endpoints, the ANCOVA model described in Section 12.10.1 will be repeated for the total body lean mass and trunk fat mass. The absolute values and mean change from baseline at each timepoint and at Week 38 for all secondary efficacy endpoints will be presented by treatment group.

In addition, correlation will be evaluated for the change from baseline in trunk fat mass and total body lean mass with the change in IGF-1 SDS level at Week 38.

Comparative statistics (p-values, 95% CI for differences) will be provided for the treatment comparison of lonapegsomatropin with placebo for all secondary efficacy endpoints. The 95% confidence intervals will be calculated for the mean treatment differences between lonapegsomatropin vs. placebo and lonapegsomatropin vs. daily somatropin.

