12.10.4. Sensitivity Analyses

To assess the robustness of the primary analysis, the following sensitivity analyses of the primary endpoint will be performed.

Sensitivity Analysis 1

Analysis of the primary endpoint will be repeated in the per-protocol population.

Sensitivity Analysis 2

Analysis of the primary endpoint will be repeated for all subjects in the ITT Population who completed 38 weeks of trial treatment regardless of intercurrent event and have a DXA assessment within final assessment window between study day 240-295.

Sensitivity Analysis 3

To assess the impact of randomized subjects using different stratification factors across dosing groups and regions, analysis of the primary endpoint will be repeated for ANCOVA model which only includes treatment arm, region (Japan versus other countries), and dosing group and baseline trunk percent fat as covariates.

Sensitivity Analysis 4

The tipping point analysis will be conducted by iteratively assigning plausible outcomes to missing values for subjects in different treatment group independently until the conclusion is reversed (eg, analyses are no longer statistically significant). The same analysis method for the primary analysis as specified in Section 12.10.1 will be applied when analyzing adjusted data generated under each plausible shift parameter. The set of shift parameters, K_1 and K_2 , will be selected to explore the space of possible missingness assumptions systematically and comprehensively. K_1 and K_2 are chosen such that the means are shifted to reduce the treatment effect and to identify the point where the p-value is tipped to be insignificant ($P >= 0.05$) (Little 2002, Rubin 1987).

The steps for conducting tipping point analysis using PROC MI are described below:

Step 1: The pre-specified set of shift parameters are K_1 for lonapegsomatropin group and K_2 for placebo group. K_1 is a set of shift parameters lying between 0 to 10 and K_2 is a set of shift parameters lying between -10 to 0. Let $k_1 \in K_1$ and $k_2 \in K_2$. Start the tipping point algorithm assuming $k_1=0$ and $k_2=0$ (under the MAR assumption, an additional step will be performed to fill in the intermittent missing data to obtain a dataset with only monotone missing pattern before implementing PROC MI using the MONOTONE option)

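### Diabetes status is a randomisation stratifier outside Japan and a factor in the protocol's ANCOVA, but the SAP's primary model and Sensitivity Analysis 3 both leave it out

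*SAP*

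**What the plan says.** **Randomisation.** Protocol section 7.1.2 names three stratification factors for all regions except Japan: dosing group, sex within the 30-to-60 no-oral-estrogen group, and "3. Diabetes mellitus status". SAP section 2 repeats the scheme and adds the exception: "In Japan, randomization will be stratified by dosing group only".

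**Protocol model.** Section 14.4.1 fixes diabetes as a term: "The ANCOVA model will include treatment arm, dose group, diabetes mellitus, and region (Japan vs. all regions except Japan) as factors". The synopsis is looser. It puts diabetes in a list of "additional factors that may include region (Japan vs. all regions except Japan" and so on. Protocol section 14 gives the final SAP precedence where the two documents differ.

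**SAP primary model.** Section 12.10.1: "The ANCOVA model will include treatment arm, region (North America, Europe, Asia-Pacific), baseline age group, gender, concomitant oral estrogen at screening in female subjects", followed by adult or childhood onset and baseline trunk percent fat. Diabetes is not there.

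**Where that model is reused.** Section 12.10.2: "the ANCOVA model described in Section 12.10.1 will be repeated for the total body lean mass and trunk fat mass". Sensitivity Analyses 1, 2 and 4 in section 12.10.4 also repeat the primary analysis.

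**Sensitivity Analysis 3.** Its purpose is "To assess the impact of randomized subjects using different stratification factors across dosing groups and regions". Its model "only includes treatment arm, region (Japan versus other countries), and dosing group and baseline trunk percent fat as covariates".

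**Elsewhere.** SAP Table 3 has baseline diabetes status (yes/no) as a subgroup. The version history in section 14.3 does not explain the choice of covariates.

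**The concern.** If randomisation is restricted on a factor that predicts the outcome, the arms are balanced on it and the treatment difference varies less from trial to trial than under simple randomisation. A model without the factor cannot see this. Its residual variance still contains the between-stratum variation, so the standard error is too large, the test is conservative and the interval is too wide. The unequal-variance adjustment in section 12.10.1 deals with variances that differ between arms, which is a separate matter.

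Nothing in the SAP model stands in for diabetes. Dosing group is largely recovered from age group plus oral estrogen, and it appears outright in Sensitivity Analysis 3. Sex is in the primary model. Diabetes is the one stratifier missing from every visible confirmatory and sensitivity model, and a subgroup analysis does not adjust for it.

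Sensitivity Analysis 3 has its own problem. The stratification factors that differ between Japan and elsewhere are diabetes and sex, and those are the two it leaves out.

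At stake are a little precision, a sensitivity analysis that does not fully answer its own question, and an unexplained gap between the protocol model and the analysis of record. Any model added after unblinding to close that gap would look post hoc.

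**Working it through.** **1. Terms side by side**

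| Term | Stratifier outside Japan | Stratifier in Japan | Protocol 14.4.1 | SAP 12.10.1 | Sensitivity Analysis 3 |
|---|---|---|---|---|---|
| Dosing group | yes | yes | yes | through age group and oral estrogen | yes |
| Sex | within group 2 | no | optional | yes | no |
| Diabetes | yes | no | yes | **no** | **no** |
| Region | – | – | Japan vs other | three regions | Japan vs other |

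**2. The plan's own figure.** SAP section 5 gives 80 per arm, a difference of 1.9, SD 3.7 and two-sided alpha 0.05. SE = 3.7 × √(2/80) = 0.585. Power = Φ(1.9/0.585 − 1.96) = 90.1%, against 90% stated. The noncentral t version gives 89.8%. The planned power reproduces and uses no covariates.

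**3. Effect of the omission.** Let *p* be the prevalence of diabetes and *d* its effect on the Week 38 change, in percentage points. The documents give neither, so both are assumed: *p* = 5–20%, *d* = 1–3. With diabetes balanced across arms:

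- Share of variance due to diabetes: s = p(1−p)d²/3.7²
- True SD of the estimated difference: 0.585 × √(1−s), while the model without diabetes still reports 0.585
- Actual alpha without diabetes: 2 × [1 − Φ(1.96/√(1−s))]
- Power without: Φ((1.9 − 1.96 × 0.585)/(0.585√(1−s)))
- Power with: Φ(1.9/(0.585√(1−s)) − 1.96)
- Excess interval width: 1/√(1−s) − 1

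Worked case, p = 0.20, d = 2: s = 0.16 × 4/13.69 = 4.67%, and the true SD is 0.585 × √0.9533 = 0.571.

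| d | p | s | Alpha without | Power without | Power with | Power forgone (points) | Interval too wide by |
|---|---|---|---|---|---|---|---|
| 1 | 5% | 0.35% | 4.96% | 90.15% | 90.21% | 0.06 | 0.2% |
| 1 | 10% | 0.66% | 4.92% | 90.18% | 90.29% | 0.11 | 0.3% |
| 1 | 20% | 1.17% | 4.87% | 90.24% | 90.44% | 0.20 | 0.6% |
| 2 | 5% | 1.39% | 4.84% | 90.27% | 90.50% | 0.23 | 0.7% |
| 2 | 20% | 4.67% | 4.47% | 90.64% | 91.41% | 0.77 | 2.4% |
| 3 | 5% | 3.12% | 4.64% | 90.46% | 90.98% | 0.52 | 1.6% |
| 3 | 20% | 10.52% | 3.83% | 91.33% | 92.97% | 1.64 | 5.7% |

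**4. Simulation without exact balance.** 240 subjects, 1:1:1, blocks of 6 within the actual strata. Assumed: 10% of subjects in Japan, dosing groups 25/50/25%, half female. The fitted three-arm model had dosing group and sex, with or without diabetes. There were 20,000 runs for alpha (Monte Carlo SE 0.15 points) and 8,000 for power.

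- 5–10% prevalence, 1 point: no detectable difference.
- 20%, 2 points: alpha 4.6% without and 5.1% with; power 90.0% and 90.8%.
- 20%, 3 points: alpha 4.1% without and 5.1% with; power 90.7% and 92.7%.

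The direction is the same. The loss of alpha is somewhat milder than in the formulas, as expected when balance is not exact.

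**5. Degrees of freedom.** The SAP model has 11 parameters: intercept 1, arm 2, region 2, age group 2, sex 1, estrogen 1, onset 1, baseline 1, and 12 with diabetes. With 240 subjects that is 229 against 228, before any adjustment for unequal variances or multiple imputation.

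**The case against.** The strongest reply is that no conclusion changes. The planned 90% power assumed no covariates, and in every scenario above the power without diabetes is still at or above 90%. The loss is therefore a gain not taken. The protocol also lets the SAP prevail, and its synopsis treats diabetes as optional. Both points are right. They limit the importance of the concern, but precedence only settles which document to correct.

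The upper magnitudes can be challenged too. A 3-point effect exceeds the 1.9-point design difference. The eligibility criteria keep out poorly controlled, recently diagnosed and complicated diabetes. Baseline fat, age and region may absorb part of the diabetes effect, and the simulation did not fit the full SAP model. The SAP also expects about 282 subjects in all, whereas these figures use 240. The 3-point rows are best read as an outer bound.

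On Sensitivity Analysis 3, dosing group is the only stratifier common to all subjects, so a reduced model built on it can be defended. But the stated purpose is the factors that differ, and the model contains none of those beyond the Japan indicator.

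Lastly, the imputation list in SAP section 11.2.6 lacks diabetes, so adding it to the analysis model leaves a covariate outside the imputation. That is true, but the list already omits sex, age group and oral estrogen, which are in the analysis model. It does not argue against the change.

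**Conclusion.** The concern holds. Diabetes is a declared stratifier outside Japan and a stated factor in protocol section 14.4.1, and no visible SAP model for the primary or key secondary endpoints adjusts for it. The consequence is mild conservatism, with no bias and no inflated type I error. With assumed prevalence of 5–20%, alpha is 4.47–4.96% and 0.06–0.8 points of power are forgone for effects of 1–2 points. At 3 points, alpha is 3.8–4.6% and 0.5–1.6 points are forgone. Across the whole range the interval is 0.2–5.7% wider than it need be. If diabetes has no bearing on the change in trunk percent fat, the cost of omitting it is nil. The change is worth making because it is nearly free, and because Sensitivity Analysis 3 otherwise falls short of its stated aim.

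**What to change.** Before unblinding:

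1. Add diabetes mellitus status (yes/no) to the ANCOVA in SAP section 12.10.1, keeping all present covariates. The change then carries to both key secondary endpoints through section 12.10.2 and to Sensitivity Analyses 1, 2 and 4.
2. Add diabetes status and sex to Sensitivity Analysis 3, next to dosing group and Japan versus other, so that it covers every stratification factor.

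No change is asked for to age group, oral estrogen or the imputation list in section 11.2.6.

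The cost is a few words in the SAP and one degree of freedom in the primary model. No new data are needed. Diabetes status is recorded for randomisation outside Japan, medical history and glycaemic tests are part of screening for all subjects, and the yes/no variable is already defined in SAP Table 3. SAP section 1 requires analysis decisions to be settled before unblinding, so the change should be made by then.
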